4.2 Method of Assignment of Patients to Cumulative Dose Groups

This is an open-label study therefore the method of assigning patients to dose groups will be based on the actual dose received by the patient.

Depending on the clinical considerations for which parenteral opioid therapy is warranted (e.g., anticipated duration of therapy, clinical site/setting), a patient could receive oliceridine using clinician-administered bolus dosing or PCA dosing. For clinician-administered bolus dosing, the oliceridine initial dose is 1 mg to 2 mg. If clinically indicated, a 1 mg supplemental dose may be administered as early as 15 minutes after the initial dose. Subsequent doses are 1 to 3 mg every 1 to 3 hours PRN based on individual patient need and previous response to oliceridine. In settings where rapid analgesia is targeted (e.g., ED or post-anesthesia care unit (PACU)), the oliceridine initial dose is 1 mg to 3 mg. If clinically indicated, 1 mg to 3 mg supplemental doses may be administered every 5 minutes PRN. Subsequent doses are 1 to 3 mg every 1 to 3 hours PRN based on individual patient need and previous response to oliceridine. For PCA dosing, the oliceridine regimen will consist of a loading dose, a demand dose, and a lockout interval without a continuous baseline infusion.

Oliceridine PCA regimen:

- Loading dose: 1.5 mg.
- Demand dose: 0.5 mg.
- Lockout interval: 6 minutes.

If clinically indicated, throughout the treatment phase, a 1 mg supplemental dose may be administered PRN, taking into account the patient's utilization of PCA demand doses, individual patient need and previous response to oliceridine.

For purposes of analysis the cumulative dose groups will be grouped in the following categories where cumulative dose group will be defined as the sum of all individual doses:

Statistical Analysis Plan

Client: Trevena, Inc.
Version #: 1.0
Version Date: 20Dec2016

Protocol/CIP #: CP130-3003

Oliceridine <= 4 mg	Oliceridine >4 to 8 mg	Oliceridine >8 to 16 mg	Oliceridine >16 to 36 mg	Oliceridine > 36 mg	All Treated Patients
------------------------	---------------------------	----------------------------	-----------------------------	------------------------	-------------------------

4.3 Blinding

This is an open-label trial in which all patients will receive oliceridine; therefore, blinding is not applicable.

4.4 Determination of Sample Size

No formal sample size calculations were made. Approximately 1000 patients will be treated with oliceridine.

5. CHANGES IN THE CONDUCT OF THE STUDY OR PLANNED ANALYSES

At the time of the writing of this document, protocol amendment 5 has been approved. For changes in the conduct of the study or planned analyses, please see the individual protocol amendments.

Client: Trevena, Inc.
 Version #: 1.0
 Version Date: 20Dec2016

Protocol/CIP #: CP130-3003
 PCN #: 2jk00017

6. BASELINE, SAFETY & TOLERABILITY, EFFICACY and PHARMACOKINETIC EVALUATIONS

6.1 Schedule of Evaluations

Procedures	Screening phase ¹ (≤ 14 days before first dose of oliceridine)	Baseline phase ¹ (Day 1)	Treatment phase (up to 14 days)		End-of-treatment phase ²				Follow-up phase ³ (Between 2 days and 3 days after completion of treatment phase)
			Predose (Day 1)	T0 to last dose of oliceridine ⁴	End-of-treatment documentation ²	Within 1 hour after completion of treatment phase ²	Within 3 hours after completion of treatment phase ²	One day after completion of treatment phase	
Informed consent ⁵	X								
Demographics	X								
Medical history	X	X							
Eligibility criteria	X	X							
ASA physical status classification ⁶	X	X							
ESI ⁷	X								
Physical examination ²	X	X			X				
Clinical laboratories ⁸	X	X					X		
Blood sample for future CYP2D6 genotyping				X					
Urine or serum pregnancy test ⁹	X	X							
Urine or serum toxicology screen ¹⁰	X								
Weight	X	X							
Height ¹¹	X								
ECG	X	X	X ¹²	X ¹³					
PK sampling ¹⁴				X					
PCA patient training ¹⁵	X	X	X	X					
Oliceridine dosing				X					
NPRS ¹⁶		X	X	X		X			
Vital signs ¹⁷	X	X	X	X		X			
MRPSS ¹⁸			X	X		X			
SOWS ¹⁹							X		
Oxygen saturation ²⁰			←-----X-----→						
Prior, concomitant medications ²¹		←-----X-----→			←-----X-----→				
AE/SAE reporting ²²		←-----X-----→			←-----X-----→				

Abbreviations: AE = adverse event; ASA = American Society of Anesthesiologists; CYP2D6 = cytochrome P450 2D6; ECG = electrocardiogram; ESI = Emergency Severity Index; MRPSS = Moline-Roberts Pharmacologic Sedation Scale; NPRS = Numeric Pain Rating Scale; PCA = patient-controlled analgesia device; PK = pharmacokinetic; SAE = serious adverse event; SOWS = Subjective Opiate Withdrawal Scale; T0 = time of first oliceridine dose.

Chiltern, International – Confidential

Page 11 of 30

Chiltern, International, All rights reserved. Reproduction or transmission to others apart from the parties involved with this document in any form or by any means is not permitted without the prior written consent of Chiltern, International.

Client: Trevena, Inc.
Version #: 1.0
Version Date: 20Dec2016

Protocol/CIP #: CP130-3003
PCN #: 2jk00017

1. When screening and baseline procedures are anticipated to occur within 48 hours of each other, they may be executed as a single procedure, unless the clinical condition of the patient has significantly changed since screening.
2. When the investigator documents that the last dose of oliceridine was administered and that the patient will no longer be treated with oliceridine, the treatment phase is complete and the end-of-treatment phase begins. A physical examination will be performed at this time.
3. Follow-up contact may be conducted in person or by telephone.
4. Procedures will be performed at any and all times during the dosing period consistent with individual patient need and institutional standards of care for a patient receiving a parenteral opioid.
5. Written informed consent.
6. If a surgical or medical patient. Refer to Section 9.3 of the protocol for the ASA scale.
7. If an ED patient. Refer to Section 9.4 of the protocol for the ESI scale.
8. Blood chemistry and hematology will be obtained using local laboratories and local laboratory range values.
9. Female patients of childbearing potential only.
10. If an ED patient.
11. Height may be obtained by measurement or patient attestation.
12. During the pre-dose period, an additional, post-surgical ECG will be performed only in surgical patients.
13. ECG will be obtained during the Treatment Phase at 60 minutes after the first dose of oliceridine, and at every 24 hours of oliceridine treatment.
14. PK samples will be collected at two times during the treatment phase: sample 1 at 30 minutes (+/- 10 minutes) after the first dose; sample 2 between 1 and 2 hours after the first dose. Unscheduled PK samples may be required. Refer to Sections 3.5.2.3 and 3.6.3 of the protocol.
15. PCA patient training is required before PCA use. If PCA is planned, training will occur during the screening and baseline phases; if PCA is started during the treatment phase, training will occur before PCA use. Training is repeated according to patient need.
16. NPRS will be measured during the pre-dose period, at 30 minutes +/-10 minutes after the first dose of oliceridine, and at any and all times during the dosing period consistent with individual patient need and institutional standards of care for a patient receiving a parenteral opioid (see Section 9.2 of the protocol).
17. Blood pressure, heart rate, respiratory rate, and temperature. Temperature will be measured at screening and baseline only.
18. Refer to Section 9.1 of the protocol for the MPRSS.
19. Refer to Section 9.5 of the protocol for the SOWS. If the patient is discharged or transferred before the time when the SOWS is to be performed, it will be performed one day after completion of the treatment phase and returned to the site by mail or in person.
20. Oxygen saturation monitoring will be continuous but will be recorded at any and all times during the dosing period consistent with individual patient need and institutional standards of care for a patient receiving a parenteral opioid. The date and time of initiation and discontinuation of continuous oxygen saturation monitoring will be recorded in the source documents.
21. Prior medications are defined as those taken before the first dose of oliceridine. Concomitant medications are defined as those taken after the first dose of oliceridine. Prior medications taken or administered within the 14 days before the first dose of oliceridine will be recorded in source and will also be recorded in eCRF. Supplemental oxygen will be recorded as a prior and/or concomitant medication.
22. AEs occurring from time of informed consent to the follow-up phase will be recorded in source and will also be recorded in eCRF if the patient receives oliceridine. SAEs occurring from time of informed consent to the follow-up phase or 7 days after the last dose of oliceridine (whichever occurs later) will be recorded in source and eCRF; ongoing SAEs after this time frame will be followed until the investigator, medical monitor, and sponsor agree that the SAE is satisfactorily resolved. SAEs considered by the investigator to be related to oliceridine, regardless of the time of onset after treatment, should be reported.

Client: Trevena, Inc.
 Version #: 1.0
 Version Date: 20Dec2016

Protocol/CIP #: CP130-3003

6.2 Time Point Algorithms

6.2.1. Baseline Assessments

Baseline assessments are listed in Section 3.6.1 of the study protocol. In general, baseline values will be defined as the last non-missing value (scheduled, unscheduled or repeat) prior to the patient receiving the first dose of oliceridine.

The following assessments will have a baseline value:

- NPRS
- Clinical Laboratories
- Vital Signs
- MRPSS Total Score
- ECG

6.2.2. Initial Setting and Condition Category

During the screening phase, the initial setting (Surgical, Medical and ED) will be recorded. The condition category for which parenteral opioid therapy was warranted will be captured using the International Classification of Diseases, 10th Revision (ICD-10) terminology.

6.2.3. Relative Day

The date of the first dose of oliceridine will be considered relative day 1, and the day before the first dose of oliceridine will be relative day -1. Relative days for events on or after the first dose will be calculated as date of event - date of first dose of oliceridine + 1. Relative days for events before the first dose will be calculated as date of event - date of first dose of oliceridine.

Study hour will be calculated relative to the first dose of oliceridine also: date/time of event - date/time of first dose of study drug.

Unless stated otherwise, if multiple observations fall within the same analysis window, the measurement closest to the midpoint of the analysis time point will be selected. If there are more than 1 assessments equal distant from the midpoint of the analysis time point, the later of the data points will be used in the analysis. All selected observations will be flagged in the listings and only the flagged observation will be used in the descriptive summary statistics over time for each parameter.

Chiltern, International – Confidential

Page 14 of 30

Chiltern, International, All rights reserved. Reproduction or transmission to others apart from the parties involved with this document in any form or by any means is not permitted without the prior written consent of Chiltern, International.

Client: Trevena, Inc.
Version #: 1.0
Version Date: 20Dec2016

Protocol/CIP #: CP130-3003

In addition to the windowed values collected during the treatment phase, the protocol specified assessments for vital signs, oxygen saturation, MRPSS and laboratory End-of-Treatment values will be summarized using descriptive statistics. The End-of-Treatment values are defined as the first observation after the end of study date/time.

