6.3.4 Vital Signs

Baseline values are defined as the last measurements taken before the first dose of oliceridine. Change from baseline will be defined as the post baseline value minus the baseline value. Vital signs will include blood pressure (BP), heart rate (HR), respiratory rate (RR), and temperature. Temperature will be measured at screening and baseline only.

Potentially clinically significant abnormal (PCSA) vital signs parameter criteria is defined below:

Parameter	Criterion value	Change relative to baseline
Systolic blood pressure (mmHg)	≥ 180 mmHg	25% increase
Systolic blood pressure (mmHg)	≤ 80 mmHg	25% decrease
Diastolic blood pressure (mmHg)	≥ 110 mmHg	25% increase
Diastolic blood pressure (mmHg)	≤ 40 mmHg	25% decrease
Pulse rate (bpm)	≥ 120 bpm	15 bpm increase
Pulse rate (bpm)	≤ 40 bpm	15 bpm decrease

Client: Trevena, Inc.
Version #: 1.0
Version Date: 20Dec2016

Protocol/CIP #: CP130-3003

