8.6.5. Vital Signs

All vital signs will be summarized for the Safety Analysis Set for each cumulative dose group and for all groups combined. Descriptive summaries (mean, SD, median, minimum, and maximum) of actual values and changes from baseline values for systolic blood pressure (SBP), diastolic blood pressure (DBP), heart rate (HR), respiratory rate (RR), and oxygen saturation will be presented at each time point defined in Section 6.2.4.

Patients meeting the PCSA criterion value or change relative to baseline will be summarized for the Safety Analysis Set for each cumulative dose group and for all groups combined also.

In addition, a listing of each vital signs parameter will be presented for each patient.

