Note: Percentages are based on the number of patients in each cumulative dose group.

Trevena, Inc.
Protocol CP130-3003CONFIDENTIAL
Page x of yTable 14.3.5.1.1 (continued)
Potentially Clinically Significant Vital Signs
(Safety Analysis Set)

PCSA Criterion	Oliceridine <= 4 mg N=XXX	Oliceridine >4 to 8 mg N=XXX	Oliceridine >8 to 16 mg N=XXX	Oliceridine >16 to 36 mg N=XXX	Oliceridine >36 mg N=XXX	All Treated Patients N=XXX
Diastolic Blood Pressure change from baseline > 25% increase	xxx (xxx.x%)	xxx (xxx.x%)	xxx (xxx.x%)	xxx (xxx.x%)	xxx (xxx.x%)	xxx (xxx.x%)
Diastolic Blood Pressure change from baseline > 25% decrease	xxx (xxx.x%)	xxx (xxx.x%)	xxx (xxx.x%)	xxx (xxx.x%)	xxx (xxx.x%)	xxx (xxx.x%)
Pulse Rate <= 40 bpm	xxx (xxx.x%)	xxx (xxx.x%)	xxx (xxx.x%)	xxx (xxx.x%)	xxx (xxx.x%)	xxx (xxx.x%)
Pulse Rate >= 120 bpm	xxx (xxx.x%)	xxx (xxx.x%)	xxx (xxx.x%)	xxx (xxx.x%)	xxx (xxx.x%)	xxx (xxx.x%)
Pulse Rate change from baseline > 15 bpm increase	xxx (xxx.x%)	xxx (xxx.x%)	xxx (xxx.x%)	xxx (xxx.x%)	xxx (xxx.x%)	xxx (xxx.x%)
Pulse Rate change from baseline > 15 bpm Decrease	xxx (xxx.x%)	xxx (xxx.x%)	xxx (xxx.x%)	xxx (xxx.x%)	xxx (xxx.x%)	xxx (xxx.x%)

Note: Percentages are based on the number of patients in each cumulative dose group.

Trevena, Inc.
Protocol CP130-3003

CONFIDENTIAL
Page x of y

Table 14.3.5.1.1 (continued)
Potentially Clinically Significant Vital Signs
(Safety Analysis Set)

PCSA Criterion	Oliceridine <= 4 mg N=XXX	Oliceridine >4 to 8 mg N=XXX	Oliceridine >8 to 16 mg N=XXX	Oliceridine >16 to 36 mg N=XXX	Oliceridine >36 mg N=XXX	All Treated Patients N=XXX
Oxygen Saturation < 90%	xxx (xxx.x%)	xxx (xxx.x%)	xxx (xxx.x%)	xxx (xxx.x%)	xxx (xxx.x%)	xxx (xxx.x%)

Note: Percentages are based on the number of patients in each cumulative dose group.

Table 14.3.6.1
Moline-Roberts Pharmacologic Sedation Scale (MRPSS) Total Score at Each Time Point
(Safety Analysis Set)

Windowed Time Point [a] Sedation	Oliceridine <= 4 mg N=XXX n (%)	Oliceridine >4 to 8 mg N=XXX n (%)	Oliceridine >8 to 16 mg N=XXX n (%)	Oliceridine >16 to 36 mg N=XXX n (%)	Oliceridine >36 mg N=XXX n (%)	All Treated Patients N=XXX n (%)
<Baseline [b]>						
1. None to Minimal	xxx (xxx.x)	xxx (xxx.x)	xxx (xxx.x)	xxx (xxx.x)	xxx (xxx.x)	xxx (xxx.x)
2. Anxiolysis	xxx (xxx.x)	xxx (xxx.x)	xxx (xxx.x)	xxx (xxx.x)	xxx (xxx.x)	xxx (xxx.x)
3. Moderate Sedation	xxx (xxx.x)	xxx (xxx.x)	xxx (xxx.x)	xxx (xxx.x)	xxx (xxx.x)	xxx (xxx.x)

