--------------------	--------------------------	-------------------------	-----------------	-----------	------------------------

Note: N = Normal; NCS = Not Clinically Significant; Csig = Clinically Significant;
Asterisk (*) denotes the value used in descriptive summary statistics.
The investigator will exercise his or her medical and scientific judgement in deciding whether an abnormal laboratory finding is clinically significant.

[a] See section 6.2.3 of the SAP for windowed time point intervals.

Trevena, Inc.
Protocol CP130-3003

CONFIDENTIAL
Page x of y

Use the same template as for Listing 16.2.7.1 for the following listings:

Listing 16.2.7.2
Laboratory Results: Hematology
(Safety Analysis Set)

Trevena, Inc.
Protocol CP130-3003CONFIDENTIAL
Page x of yListing 16.2.8
12 Lead Electrocardiogram Results
(Safety Analysis Set)

Patient ID/Sex/Age/Cumulative Dose Group: 1001/Male/30/ Oliceridine <= 4 mg

Assessment Date/Time	Windowed Time Point[a]			RR	QRS	QT	QTcF	Interpreta tion	Abnormal, Sepcify
		Heart Rate (beats/min)	PR Interval (msec)	Interval (msec)	Interval (msec)	Interval (msec)			

Note: Csig = Clinically Significant; NCS = Not Clinically Significant.

Asterisk (*) denotes the value used in descriptive summary statistics.

Trevena, Inc.
Protocol CP130-3003

CONFIDENTIAL
Page x of y

Listing 16.2.9
Subjective Opioid Withdrawal Scale (SOWS)
(Safety Analysis Set)

Cumulative Dose Group: Oliceridine <= 4 mg

Patient ID/Sex/Age	Assessment Date/Time	Symptom	Intensity Rating [a]
--------------------	----------------------	---------	----------------------

[a] 0 = Not at all; 1 = A little; 2 = Moderately; 3 = Quite a bit; 4 = Extremely.

Trevena, Inc.
Protocol CP130-3003

CONFIDENTIAL
Page x of y

Listing 16.2.10
Physical Examination
(Safety Analysis Set)

Cumulative Dose Group: Oliceridine <= 4 mg

Patient ID/Sex/Age

Assessment Date/Time

Changes From Previous Visit?

Trevena, Inc.
Protocol CP130-3003

CONFIDENTIAL
Page x of y

Listing 16.2.11
Moline-Roberts Pharmacologic Sedation Scale Score
(Safety Analysis Set)

Cumulative Dose Group: Oliceridine <= 4 mg

Patient ID/Sex/Age	Assessment Date/Time	Windowed Time Point [a]	Total Score
--------------------	----------------------	-------------------------	-------------

Note: Asterisk (*) denotes the value used in descriptive summary statistics.

[a] See section 6.2.3 of the SAP for windowed time point intervals.

Trevena, Inc.
Protocol CP130-3003CONFIDENTIAL
Page x of yListing 16.2.12.x

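### No planned table counts patients who ever reached MRPSS 5-6 or a low respiratory rate, because the by-time tables keep one midpoint-nearest reading per window

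*SAP*

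**What the plan says.** SAP 6.2.4 assigns vital signs, oxygen saturation and MRPSS to windows of 0-1, 1-4, 4-12, 12-24, 24-36, 36-48, 48-72 and 72-96 hours, with an open-ended window from 96 hours. Within each window, "if multiple observations fall within the same analysis window, the measurement closest to the midpoint of the analysis time point will be selected". Ties go to the later reading, and "only the flagged observation will be used in the descriptive summary statistics over time for each parameter". The rule allows for exceptions stated elsewhere, but none is stated for MRPSS or respiratory rate. One further reading is summarised: "The End-of-Treatment values are defined as the first observation after the end of study date/time".

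- **MRPSS.** The only table is mock Table 14.3.6.1, "Moline-Roberts Pharmacologic Sedation Scale (MRPSS) Total Score at Each Time Point". It counts patients at levels 1 to 6 at baseline and in each window, with no worst or overall row. SAP 8.6 has no MRPSS subsection.
- **Respiratory rate.** SAP 8.6.5 plans descriptive statistics only: "respiratory rate (RR), and oxygen saturation will be presented at each time point defined in Section 6.2.4". SAP 6.3.4 introduces its threshold table with "Potentially clinically significant abnormal (PCSA) vital signs parameter criteria is defined below", and the rows are systolic pressure, diastolic pressure and pulse rate. Mock Table 14.3.5.1.1 adds "Oxygen Saturation < 90" per cent. Neither has a respiratory-rate row.
- **Listings.** Listings 16.2.6.1 (vital signs) and 16.2.11 (MRPSS) show every reading. Their footnote reads "Asterisk (*) denotes the value used in descriptive summary statistics", so unselected readings are listed but not tabulated.

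Protocol 3.1.4 sets no charting schedule for the dosing period; frequency follows patient need and the institution's standard of care. Protocol 6.3 commits to a descriptive summary of clinically significant changes in vital signs and sedation scores.

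**The concern.** The primary objective is the safety of an opioid. Protocol 1.3.1 measures safety as the incidence of adverse events, including those related to vital signs and sedation scores. A count from measured data is therefore the natural check on what investigators chose to report. For oxygen saturation the plan has that check. For sedation depth and respiratory rate it does not, and the SAP does not say how the Protocol 6.3 commitment will be met for these two measures.

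Selection by closeness to the midpoint ignores severity. Brief deep sedation or slow breathing between selected readings will be missing from the by-time tables. The count of affected patients cannot be rebuilt from Table 14.3.6.1, because adding windows counts some patients more than once and still leaves out unselected readings.

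Elsewhere the SAP does provide such rows: a worst post-baseline value for laboratory results, a row for patients with at least one hepatic finding, an overall row for QTcF thresholds, and a row for at least one clinically significant ECG. Leaving out sedation and respiratory rate is an inconsistency within the plan.

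**Working it through.** The plan states no figure on this point, so there is none to reproduce. The check has three parts.

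**1. Is there a patient-level count anywhere?**

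| Measure | By-time table | Worst, overall or any-time row |
|---|---|---|
| Laboratory values | Yes | Yes (SAP 8.6.4) |
| Hepatic thresholds | Yes | Yes (Table 14.3.4.1) |
| QTcF thresholds | Yes | Yes (Table 14.3.7.1.1) |
| ECG findings | Yes | Yes (Table 14.3.7.1.2) |
| Blood pressure, pulse, oxygen saturation | Yes | Yes, PCSA counts (Table 14.3.5.1.1) |
| Respiratory rate | Yes | None |
| MRPSS | Yes | None |

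This result needs no assumption about charting.

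**2. How often would an episode reach the by-time table?** Inputs from SAP 6.2.4: the windows, their midpoints and the tie rule; the open-ended window has its stated midpoint of 96 hours. Assumed, because the documents give neither: evenly spaced readings every *s* hours until the end of a stay of *L* hours, with the first reading moved from 0 to just under *s* in 5-minute steps, and an episode equally likely at any reading.

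Share kept = selected readings / all readings. Ranges are over the time of the first reading.

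| Stay | Hourly | 2-hourly | 4-hourly |
|---|---|---|---|
| 6 h | 3/6 = 50% | 2/3 to 3/3 = 67-100% | all kept |
| 24 h | 4/24 = 17% | 3/12 to 4/12 = 25-33% | 3/6 = 50% |
| 72 h | 7/72 = 10% | 6/36 to 7/36 = 17-19% | 6/18 = 33% |
| 120 h | 9/120 = 8% | 8/60 to 9/60 = 13-15% | 8/30 = 27% |

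For 24 hours with sparser charting: 6-hourly 2/4 to 3/4 = 50-75%; 8-hourly 2/3 to 3/3 = 67-100%.

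Longer episodes are kept more often. For *k* consecutive readings over 24 hours, the share with at least one selected is:

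- *k* = 2: hourly 7/23 = 30%; 2-hourly 5/11 to 6/11 = 45-55%; 4-hourly 4/5 to 5/5 = 80-100%.
- *k* = 4: hourly 11/21 to 12/21 = 52-57%; 2-hourly 8/9 = 89%.

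Worked example: hourly readings from time 0 over 24 hours. The 0-1 h window holds only hour 0. In the 1-4 h window, hours 2 and 3 are equally far from 2.5, so the later, hour 3, is taken. The next two windows give hours 8 and 18. A patient at MRPSS 5 at hours 5 and 6 only appears in Listing 16.2.11 and not among the level-5 counts in Table 14.3.6.1.

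**3. What would a worst-value row bring with it?** The chance of ever crossing a threshold grows with the number of readings. Assume a constant 0.5% chance per independent reading and no dose effect:

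- P(ever) = 1 - (1 - 0.005)^n
- n = 6: 1 - 0.995^6 = 3.0%
- n = 24: 1 - 0.995^24 = 11.3%
- n = 72: 1 - 0.995^72 = 30.3%

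The columns are cumulative-dose groups (SAP 4.2), so longer treatment alone could look like a dose trend. The fix has to allow for this.

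**The case against.** The midpoint rule is an ordinary choice for trends and applies only to statistics over time. That is right, and the rule should stay; the defect is the missing rows.

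The protocol's safety measure is adverse events, and those tables do not use midpoint selection. Protocol 4.3.2 also requires dosing to be interrupted for advancing sedation or respiratory signs, so serious episodes are likely to be noticed. This has force, but 4.3.2 governs dosing and not tabulation. Under Protocol 4.1.3 an abnormal assessment becomes an adverse event only if the investigator judges it clinically significant. Protocol 4.1.1 lets anticipated signs in surgical and medical patients go unrecorded unless they exceed expectation.

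Nothing is lost from the database, there is no hypothesis test to bias, and the oxygen-saturation row already gives one respiratory count. All true. This limits the severity, but line listings for about 1000 patients are not a summary.

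The size is unknown: the illustrations run from 8% to 100% kept, and charting driven by patient need may cluster around an episode. This stands.

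The earlier abdominoplasty study in Protocol 1.1, where hypoventilation was seen in 15% and 31% of patients on the two oliceridine regimens, is weak support. That definition is a composite requiring persistence, and placebo had 10%. It shows only that the programme has treated reduced respiratory rate as relevant.

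**Conclusion.** The concern holds. Followed as written, the SAP yields a sedation table that can omit recorded MRPSS 5-6 readings, no threshold count for respiratory rate, and no stated way to meet the Protocol 6.3 commitment for either measure. That rests on the SAP text and mock tables alone.

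The size of the loss rests on assumed, evenly spaced charting. It is large for brief episodes under frequent charting and long stays, and small or nil for short stays, sparse charting or prolonged episodes. It should be fixed before database lock, but it does not threaten the study: the readings are collected and listed, and reported events reach the adverse-event tables.

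**What to change.** Keep the midpoint rule for trends and make these additions:

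- A worst post-baseline row using all readings from first dose through the End-of-Treatment reading: maximum MRPSS in Table 14.3.6.1 (levels 1 to 6, and 5-6 combined) and minimum respiratory rate in Table 14.3.5.1.
- A respiratory-rate criterion in SAP 6.3.4 and Table 14.3.5.1.1, with the cut-off set by the sponsor before lock. The documents give none.
- A short MRPSS subsection in SAP 8.6 naming these rows.
- Median number of readings and median treatment duration per cumulative-dose group beside the worst-value rows, with a footnote that differences across dose columns are not dose effects.
- A footnote that lower MRPSS levels may reflect normal sleep, which the scale builds in (Protocol 3.6.2.4). The combined 5-6 count is the more useful figure.
- A clarification that PCSA counts use all post-baseline readings. Flagging is limited to statistics over time and that table has no time points, but the SAP should say so.

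The cost is a few sentences and table rows, with no new data. The tables become longer, the rates may look less favourable, and ever-reached rates without a comparator need the cautions above.
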